1.0 Study Summary

Study Title	Effects of narratives on demand for low and high ventilated cigarettes and substitution for alternative products.
Study Design	In a between-group within-subject repeated measures design, participants will be randomized to one of three groups (narrative, fact sheet, or control) and complete five ETM conditions, which include six trials assessing different cigarette prices: a) high-ventilated cigarette alone, b) low-ventilated cigarette alone, c) high- and low-ventilated cigarette with high-ventilated cigarettes increasing in price, d) high- and low-ventilated cigarette with low-ventilated cigarettes increasing in price, and e) usual, high- and low-ventilated cigarette with usual cigarettes increasing in price.
Primary Objective	To compare the effects of narratives on demand for low and high ventilated cigarettes and substitution for alternative products in the Experimental Tobacco Marketplace.
Secondary Objective(s)	N/A
Study Population	Ventilated cigarette (16 to 38%) smokers
Sample Size	N = 90 completers
Research Intervention(s)/ Investigational Agent(s)	A narrative or a fact sheet about the negative consequences of smoking high-ventilated cigarettes and a survey consisting of questionnaires and behavioral tasks.
Study Duration for Individual Participants	Session 1: Consent and Assessments (approximately 2h00). Session 2: Experimental Tobacco Marketplace (approximately 1h30) Session 3: Follow-up (approximately 30 minutes)
Acronyms and Definitions	ETM: Experimental Tobacco Marketplace FBRI: Fralin Biomedical Research Institute VTCRC: Virginia Tech Corporate Research Center

2.0 Objectives

2.1 *Describe the purpose, specific aims, or objectives of this study:*

Purpose: To compare the effects of narratives on demand for low and high ventilated cigarettes and substitution for alternative products in the Experimental Tobacco Marketplace.

2.2 *State the hypotheses to be tested:*

22-432 Effects of narratives on demand for low and high ventilated cigarettes and substitution for alternative products.

The primary hypothesis is that narratives will decrease purchases of ventilated cigarettes and increase purchases of alternative products compared to the control narrative (fact sheet).

3.0 Background

3.1 *Summarize the relevant prior research on this topic and gaps in current knowledge within the field of study:*

The Food and Drug Administration (FDA) was granted authority in 2009 to establish tobacco product standards if those standards are reasonably expected to benefit the public health. One product feature that could be changed is cigarette filter ventilation. A recent review examined the effects of cigarette filter ventilation and concluded that filter ventilation, by changing how a cigarette burns, yields more mutagens and carcinogens, and results in greater puff volume and possibly depth of inhalation, which has led to increases in peripheral lung adenocarcinomas (1). This, along with the ability to manipulate systemic levels of nicotine by altering smoking behavior, as well as misconceptions about the lower toxicity of filter ventilation, may have also contributed to the use, appeal, and abuse liability of ventilated cigarettes. The extent to which commercial cigarettes are ventilated vary substantially in the market by brand, ranging from 0 to 80%. However, smokers compensate for the lower nicotine yields associated with higher ventilation by varying their puffing behavior, number of cigarettes per day, and blocking some portion of the ventilation holes. This compensatory behavior exposes smokers to more tobacco smoke constituents than would be indicated by machine smoking tests. Regulatory action that reduces or eliminates cigarette ventilation would not only reduce exposure to smoke constituents by increasing nicotine yield per cigarette, but also change the smoker's experience, likely resulting in harsher taste that may be proportional to the ventilation in a given cigarette brand. The potentially large effect on taste and preference corresponding to cigarette ventilation could alter the appeal and abuse liability of these products and could inform regulatory actions. However, eliminating filter ventilation raises a variety of questions that constitute a gap in our knowledge and must be answered to assess the potential for adverse unintended consequences of removing filter ventilation. We will explore these questions within a behavioral economic framework.

Behavioral economic demand analyses can be used to understand the level of motivation to consume a product on either an individual or small group level, including cigarettes (2,3). This level of analysis allows for experimental manipulations to be made on variables of interest. By quantifying how consumption decreases as costs increase to obtain and consume a product, important indices of demand are obtained. These indices can be grouped into two main measures of consumption, demand intensity and demand elasticity, which are associated with use level and dependence severity (3,4,5,6). Demand intensity is the amount of the commodity consumed when available at very low cost (approaching free), and demand elasticity quantifies the degree to which the individual is willing to increase monetary or effort-based expenditures to maintain the same level of consumption as costs increase. Elasticity of demand has been shown to be a characteristic of the drug itself and independent of drug dose for many drugs including nicotine (2,7,8).

22-432 Effects of narratives on demand for low and high ventilated cigarettes and substitution for alternative products.

While drug demand plotted as a function of unit price has been often shown to be a function of the total drug consumed, some of our prior research with cigarette demand calls this conclusion into question. A prior study we conducted (9) compared conventional cigarettes to denicotinized cigarettes. We found that, if these denicotinized cigarettes were the only tobacco product available, the denicotinized cigarettes had comparable demand to nicotinized cigarettes. If both were available, however, participants preferred the nicotinized cigarettes. This suggests that cigarette demand is not strictly regulated by nicotine dose, and that there is substantial abuse liability associated with other aspects of cigarettes (e.g., sensory components) apart from any nicotine content. Relevant to this point, we conducted a pilot study, where conventional ventilated cigarette smokers purchased either their usual cigarettes (ventilated) or their usual cigarettes with the filter vents blocked. When each cigarette type was available alone in separate sessions, demand for both products was very similar. However, in a separate session in which both cigarette types were available concurrently at equivalent unit prices, ventilated cigarettes were clearly preferred at all prices. These findings suggest that to fully understand the abuse liability of cigarettes will require that they are studied in contexts where other products are available (e.g., substitution).

Substitution is defined as an increase in the consumption of a constant-priced product while the cost of a different commodity is increased. For example, we have shown that as the price of conventional cigarettes is increased and its consumption decreased, the consumption of nicotine gum increased even though its price remained constant (10). Substitution defines one end of a continuum of interactions between two commodities. At the other end of that continuum, commodities can also function as complements. Complementarity refers to the decreased consumption of a constant-priced product in response to an increase in the price of a different commodity. For example, the research team has previously shown that as the price of cigarettes increased, consumption of coffee decreased even though its price remained constant (11). Between these two extremes is independence, which occurs when changes in the price of one commodity have little or no effect on consumption of another commodity where price has remained unchanged. Substitution, complementarity, and independence are measured by cross-price elasticity of demand and are represented by values that are positive, negative, or near zero, respectively. Studies to date have almost exclusively examined only pairs of products and, in even fewer cases, three concurrently available commodities. For example, in one of our studies smokers had access to conventional cigarettes, denicotinized cigarettes, and nicotine gum¹³. When the price of conventional cigarettes increased, consumption of both denicotinized cigarettes and nicotine gum increased even though their prices were fixed. Thus, denicotinized cigarettes and nicotine gum functioned as substitutes for conventional cigarettes. Indeed, by concurrently using both products, the smoker could reproduce both the central and sensory effects of standard cigarettes by consuming the denicotinized cigarette (i.e., sensory effects) and nicotine gum (i.e., central effects). Importantly, denicotinized cigarettes functioned as a better substitute than gum (the use of denicotinized cigarettes increased the most). This effect could not have been predicted from the individual demand curves with these commodities. Only when they were measured together did these complex interactions emerge. Lastly, in this experiment consumption of conventional cigarettes was greatest

22-432 Effects of narratives on demand for low and high ventilated cigarettes and substitution for alternative products.

when it was the only available product, and was least when denicotinized cigarettes or both alternatives were available. This finding demonstrates that cigarette demand was altered by the presence of alternative products and that under some conditions multiple products will be used concurrently. However, this and similar studies are constrained by arbitrary circumstances of the laboratory, such as required nicotine deprivation, constrained consumption of a product (e.g., 1 cigarette puff per self-administration), long and numerous sessions (e.g., one, 3-hour session for each price examined). As such, these methods cannot and do not come close to replicating the ever more complex tobacco marketplace and underscore the gap in the understanding of how to examine these relationships among a large number of products that approximate the real world.

To address this methodological gap and to inform how various products may interact, we have developed and tested a novel method called the Experimental Tobacco Marketplace (ETM). The ETM is similar to an online store, that displays pictures, information, and prices for several tobacco/nicotine products. In a recent study of ours (14), smokers were endowed with an amount of money comparable to their weekly tobacco purchases. They then made tobacco product purchasing decisions while the price of conventional cigarettes was varied and the price of 5 other tobacco products remained constant. Purchasing decisions from one, randomly selected cigarette price was actualized and smokers were provided the products purchased and any unspent account balance. Smokers returned one week later to report tobacco/nicotine use and return unused products for a refund. Cigarette consumption decreased as a function of price. As the price of cigarettes increased, consumption of snus, electronic cigarettes, and nicotine lozenges showed the greatest substitution. Importantly, this approach moves beyond the constraints of previous laboratory studies by permitting the study of tobacco/nicotine preference and consumption under conditions that typically occur in most smokers' lives, including not being nicotine deprived, consuming the products in their natural environment, selecting the products they wish from a large number of products, and consuming the products while engaging in normal daily activities.

As part of this grant, one previous study [9] has examined the effect of removing filter ventilation on nicotine product consumption. Our findings show that initial exposure to unventilated cigarettes reduced the number of cigarettes purchased and increased exploration of alternative tobacco products. However, successive exposure to unventilated cigarettes led to increased cigarette purchases. This suggests that regulating filter ventilation may initially increase exploration of alternative tobacco products but lead to exploitation of unventilated cigarettes over time. Moreover, tobacco control strategies could take advantage of this transition period when smokers seek information on unfamiliar products to implement harm reduction strategies.

6. [name] WK, Pope DA, Kaplan BA, et al. Electronic cigarette substitution in the experimental tobacco marketplace: A review. *Prev Med* 2018;117:98–106. doi:10.1016/j.ypmed.2018.04.026

3.3 Based on the existing literature, provide the scientific or scholarly rationale for and significance of your research and how will it add to existing knowledge:

No study to date has experimentally examined the effects of narratives on demand for high- and low-ventilated cigarettes and substitution for other tobacco products. The rationale for this specific proposal is to explore prospectively possible ways to educate smokers about the negative consequences of smoking high-ventilated cigarettes and the

22-432 Effects of narratives on demand for low and high ventilated cigarettes and substitution for alternative products.

potential benefits of quitting and transitioning to less harmful products. The results might inform tobacco control policies.

Study Endpoints

3.4 *Describe the primary and secondary **study** endpoints. See links below for discussion of study endpoints and how they may differ from study objectives. These are most common in clinical trials but are sometimes applicable to other types of biomedical research, as well as social, behavioral, or educational research. See link below for a discussion.*

https://docs.google.com/document/d/1Wocz7K7a0hCQJPPO_khh511SQQjhGDDGHzcOPRHR5Tw/edit?usp=sharing

Substitutability: the two groups will be compared to assess whether substitutability with tobacco products occurs as a function of the intervention and cigarette price.

3.5 *Describe any primary or secondary **safety** endpoints. These should be included for all studies that are greater than minimal risk. (Minimal risk: The probability and magnitude of harm or discomfort anticipated in the research that are not greater in and of themselves than those ordinarily encountered in daily life or during the performance of routine physical or psychological examinations or tests.):*

This study will recruit adults who regularly smoke high-ventilated cigarettes. This study's procedures are not designed to increase daily nicotine use and we do not anticipate any increased risk to participants directly from this study, although there are risks of nicotine use and these are included in the risk section of this protocol and consent.

4.0 Study Design and Statistical Analysis Plan

4.1 *Describe the basic study design/approach (e.g., qualitative study using five focus groups of first year students to describe assimilation into the university community; randomized controlled trial of a behavioral change intervention to increase dietary intake of whole grains; pre- post-test evaluation of new pedagogical techniques to improve adult literacy):*

In a between-group within-subject repeated measures design, participants will be randomized to one of three groups (narrative, fact sheet, or control) and complete five ETM conditions, which include six trials assessing different cigarette prices: a) high-ventilated cigarette alone, b) low-ventilated cigarette alone, c) high- and low-ventilated cigarette with high-ventilated cigarettes increasing in price, d) high- and low-ventilated

22-432 Effects of narratives on demand for low and high ventilated cigarettes and substitution for alternative products.

cigarette with low-ventilated cigarettes increasing in price, and e) usual, high- and low-ventilated cigarette with usual cigarettes increasing in price.

4.2 *Describe corresponding data analysis plan/approach (e.g., content analysis of focus group transcripts; descriptive analysis followed by linear regression modeling; nonparametric analysis of pre- and post-test measures):*

A within-between subject analysis of variance (ANOVA) will test for differences in substitution and demand measures between groups (narrative, fact sheet, and control) and condition (e.g., high-ventilated cigarettes alone). We will test for the interaction between group and condition, suggesting a difference in how each group responds to different conditions. Order effects will be included in all models to account for the balanced Latin square design for counterbalancing the ETM conditions within the session. We will perform post-hoc contrasts to compare groups, based on our hypothesis.

Additional analyses might be conducted.

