13.0 Number of Subjects

13.1 Indicate the total number of subjects to be enrolled and how this number was determined (e.g., sample size calculation [show], number of available subjects in a finite pool, number of tests funding award would allow):

In this study, we require n=90 (N=100 accounting for 10% attrition) participants to complete the study when using repeated measures with three groups and two measurements per participant.

Our sample sizes are based on a repeated-measures within-between interaction ANOVA design using medium effect size ($f=0.25$) and 95% power. To account for multiple testing, we will control for five comparisons in each experiment; therefore, we use an alpha of 0.01.

We have been successfully recruiting cigarette smokers in our community for the past 10 years. Based on our experience with prior studies, we anticipate that 10% of participants don't complete the study.

22-432 Effects of narratives on demand for low and high ventilated cigarettes and substitution for alternative products.

13.2 If this is a multi-site study, indicate the number of subjects to be enrolled at this site and the total to be enrolled from all sites:

N/A

13.3 If applicable, indicate the number of potential subjects you expect to screen for enrollment, and the number of subjects you will need to complete the research procedures:

As stated previously, we have developed and are currently using a separate pre-screening protocol, which occurs prior to enrolling participants into our research protocols. As described above, we anticipate enrolling 100 participants to complete a total of 90 participants.

13.4 If the study has more than one procedure, indicate the total number of subjects to undergo each procedure separately:

All participants will undergo all three sessions unless they withdraw consent.

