**NCT: NCT05487625**

**Document date: 09/13/2022**

### ***Study Design and Statistical Analysis plan***

In a between-group within-subject repeated measures design, participants will be randomized to one of three groups (narrative, fact sheet, or control) and complete five ETM conditions, which include six trials assessing different cigarette prices: a) high-ventilated cigarette alone, b) low-ventilated cigarette alone, c) high- and low-ventilated cigarette with high-ventilated cigarettes increasing in price, d) high- and low-ventilated cigarette with low-ventilated cigarettes increasing in price, and e) usual, high- and low-ventilated cigarette with usual cigarettes increasing in price.

A within-between subject analysis of variance (ANOVA) will test for differences in substitution and demand measures between groups (narrative, fact sheet, and control) and condition (e.g., high-ventilated cigarettes alone). We will test for the interaction between group and condition, suggesting a difference in how each group responds to different conditions. Order effects will be included in all models to account for the balanced Latin square design for counterbalancing the ETM conditions within the session. We will perform post-hoc contrasts to compare groups, based on our hypothesis.

Additional analyses might be conducted.

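### The 95% power in section 13.1 belongs to a two-measurement group-by-condition interaction, not to the narrative-versus-fact-sheet difference hypothesised in section 2.2

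*Protocol*

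**What the plan says.** Section 2.2 of the protocol hypothesises that "narratives will decrease purchases of ventilated cigarettes and increase purchases of alternative products", with the fact sheet as the comparator.

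Section 4.2, repeated in the SAP, plans a within-between ANOVA with group and condition as factors on substitution and demand outcomes. It continues: "We will test for the interaction between group and condition, suggesting a difference in how each group responds to different conditions". Group comparisons then follow: "We will perform post-hoc contrasts to compare groups, based on our hypothesis".

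The design has five purchasing conditions. The SAP's list begins "a) high-ventilated cigarette alone, b) low-ventilated cigarette alone, c) high- and low-ventilated cigarette with high-ventilated cigarettes increasing in price". Condition d offers both types with the low-ventilated price rising, and condition e adds the usual cigarette, whose price rises.

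On sample size, section 13.1 says: "Our sample sizes are based on a repeated-measures within-between interaction ANOVA design". It uses f=0.25, 95% power and alpha 0.01 (five comparisons), and describes "repeated measures with three groups and two measurements per participant". It does not say which two measurements these are, and it gives no correlation between them. No power is stated for any comparison of groups.

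**The concern.** Hypothesis 2.2 concerns the level of purchasing in one group against another. A group-by-condition interaction asks whether that gap changes from condition to condition. If the narrative shifts purchasing by the same amount throughout, which 2.2 allows, the interaction carries no information about it.

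The trial would then be described as having 95% power while the comparison that answers its hypothesis has much less. A null interaction could be reported as evidence that narratives do not work, in a study whose results, according to section 3.3, may inform tobacco policy.

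A second, smaller gap is that the plan does not tie outcomes to conditions. No named cigarette is sold in all five, so the reader cannot tell which levels enter which model.

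**Working it through.** **Inputs.** From section 13.1: k=3 groups, N=90 completers, m=2 measurements, f=0.25, alpha 0.01. From section 4.1: five conditions. Assumed, because the documents give no value: correlation rho between repeated measures of 0.5 (range 0.3 to 0.7), and sphericity for the power figures.

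**1. The plan's own figure.** Interaction noncentrality is lambda = f²·N·m/(1−rho), with (k−1)(m−1) and (N−k)(m−1) degrees of freedom.
- lambda = 0.0625 × 90 × 2 / 0.5 = 22.5 on 2 and 87 df, so power is 95.7%.
- The smallest N for 95% is 88, or 90 in equal groups, and 90/0.9 = 100 enrolled. Section 13.1 reproduces.
- Power is 84.5% at rho 0.3 and 99.9% at rho 0.7.
- At rho 0.5, four levels give 99.9% and five levels over 99.9%.

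**2. The group effect.** A participant's mean over m conditions has variance (1+(m−1)rho)/m relative to a single measurement, so lambda = f²·N·m/(1+(m−1)rho) on 2 and 87 df. Using f=0.25 here is an assumption, since 13.1 states it for the interaction. With m=2 and rho 0.5, lambda = 11.25/1.5 = 7.5 and power is 43%.

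**3. Narrative versus fact sheet.** Take group means (d, 0, 0). Their standard deviation is d√2/3, so f=0.25 corresponds to d = 0.25 × 3/√2 = 0.53. The contrast has noncentrality d/√[((1+(m−1)rho)/m)·(2/30)] on 87 df. With m=2 and rho 0.5 this is 0.53/√0.05 = 2.37 against a two-sided 0.01 critical value of 2.63, and power is 40%.

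Power with 90 completers:

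| Test | Alpha | Conditions averaged | rho 0.3 | rho 0.5 | rho 0.7 |
|---|---|---|---|---|---|
| Group effect | 0.01 | 2 | 50% | 43% | 37% |
| Group effect | 0.01 | 4 | 68% | 52% | 41% |
| Group effect | 0.01 | 5 | 73% | 55% | 42% |
| Narrative v fact sheet | 0.01 | 2 | 47% | 40% | 35% |
| Narrative v fact sheet | 0.01 | 4 | 64% | 49% | 39% |
| Narrative v fact sheet | 0.01 | 5 | 68% | 51% | 40% |
| Group effect | 0.05 | 2 | 74% | 67% | 61% |
| Group effect | 0.05 | 5 | 89% | 77% | 67% |
| Narrative v fact sheet | 0.05 | 2 | 71% | 65% | 60% |
| Narrative v fact sheet | 0.05 | 5 | 86% | 75% | 64% |

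**4. An equal effect in every condition.** A constant shift cancels from every within-person difference between conditions, so the interaction's noncentrality is zero. In simulation (40,000 trials, three groups of 30, shift d=0.53, rho 0.5, alpha 0.01), the interaction rejected in 1.02% of trials with five levels, 1.00% with four (a, c, d, e) and 1.06% for a versus c. The group test rejected in 55%, 52% and 42%.

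**5. Which outcome exists where.**
- Quantity purchased: high-ventilated in a, c, d, e; low-ventilated in b, c, d, e; usual in e only.
- Own-price demand (section 3.1: "These indices can be grouped into two main measures of consumption, demand intensity and demand elasticity"): high-ventilated in a and c; low-ventilated in b and d.
- Cross-price measures (section 3.1: "Substitution, complementarity, and independence are measured by cross-price elasticity of demand"): low-ventilated in c and e; high-ventilated in d and e.
- Five levels suit only outcomes defined in all five, such as whichever cigarette rises in price, or alternative products if these are on sale in a and b as well. Section 6.2 lists them as purchasable but does not settle that.

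**6. Sphericity.** With more than two levels and unequal correlations, the uncorrected interaction test at nominal 0.01 rejected in 0.010 to 0.028 of simulated null trials with five levels and 0.009 to 0.022 with four. With five levels, Greenhouse-Geisser gave 0.009 to 0.012. The group effect is unaffected (0.009 to 0.011).

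**The case against.** The strongest reply is that the group comparison is already planned. The ANOVA in section 4.2 tests groups as well as conditions, and its contrasts are tied to the hypothesis. That stands: a reader might infer that the group difference is missing or left entirely to post-hoc work, and the text does not support this. What is absent is its designation as the test of 2.2 and a power statement.

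A reader might also infer from the condition list that the five-level model cannot be fitted. The plan never says that all five levels are applied to one named cigarette, and it refers to models in the plural. The two measurements in 13.1 would fit a versus c or b versus d, although the plan does not make that link. The gap is missing detail, not an impossible model.

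The low power figures depend on alpha 0.01 and on borrowing f=0.25. A single prespecified contrast might be given alpha 0.05. Power then rises to about 65% to 77% at rho 0.5, which narrows the gap without closing it.

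Finally, section 1.0 describes materials about the harms of high-ventilated cigarettes, so effects may well differ by cigarette type. The interaction is therefore a legitimate question. It is still a different one from 2.2, and an equal effect cannot be excluded. Section 3.4 names substitutability compared across groups, intervention and price, but assigns no test or power to it.

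**Conclusion.** The point holds. The stated 95% power is correct for a two-level interaction at a correlation near 0.5, and it does not carry over to the hypothesis in 2.2. At alpha 0.01 the group effect has 43% to 55% power at rho 0.5 (37% to 73% over rho 0.3 to 0.7), and narrative versus fact sheet has 40% to 51% (35% to 68%). At alpha 0.05 the two together span about 65% to 77% at rho 0.5 (60% to 89% over the range), still below 95%.

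These figures assume the correlations shown, f=0.25 for the group effect (d=0.53 for the contrast) and 30 completers per group. A reader might infer that 90 is an arithmetical error or too few for the interaction. At rho 0.5 it is neither. The blindness of the interaction to an equal effect does not depend on these assumptions.

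The mapping of outcomes to conditions is a matter of specification. The sphericity point is minor and concerns the condition main effect as well as the interaction.

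**What to change.** 1. Designate the narrative-versus-fact-sheet contrast, averaged over the conditions in which the outcome is defined, as the test of 2.2. Keep group-by-condition as a separate question, and state that a null interaction is not evidence of no narrative effect.
2. Reword 13.1 so that 95% refers only to the two-level interaction at its assumed correlation. Add the power of the group contrast at its assigned alpha. Do not enlarge the trial.
3. List each model's outcome, product, conditions and tested term. Use a, c, d, e for high-ventilated quantity; b, c, d, e for low-ventilated quantity; a and c, or b and d, for own-price demand. For cross-price measures, note that the available pairs change both the priced cigarette and the choice set. Reserve five levels for outcomes defined in all five, and state whether alternative products are on sale in a and b.
4. For any within-participant factor with more than two levels, use Greenhouse-Geisser or a mixed model with unstructured covariance.

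The cost is SAP wording and modest programming, with no new data. The downside is a less favourable stated power and slightly less interaction power after correction (five levels, rho 0.5, epsilon 0.63: 99.1% instead of over 99.9%).
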